2. A dose-response relationship for disease-free survival in stage I NSCLC has been reported. Dosoretz et al showed that actuarial disease-free survival at 2-years was 50%, 33%, 22%, and < 20% with 70 Gy (n=4), 60-69 Gy (n=116), 50-59 Gy (n=26), and < 50 Gy (n=6), respectively. The actuarial risk for local failure at 3 years was 33%, 60% and 58% for > 70 Gy (n=4), 60-69 Gy (n=91) and 50-59 Gy (n= 19), respectively.
3. The preliminary data from the RTOG 9311 (Bradley et al) phase I dose escalation study showed that acute toxicity rates were acceptable for dose up to 90.3 Gy (less than 15% grade ≥ 3 pneumonitis and no esophagitis). However, late toxicities were more pronounced. Late grade ≥ 3 radiation pneumonitis occurred at a rate of 15% for patients with a V20<25% for patients treated to dose levels of 77.4 Gy or above with fraction size of 2.15 Gy. For patients with a V20 of 25-37%, late grade ≥ 3 pneumonitis occurred at the rate of 15% for the doses of 70.9 Gy or above. Late grade ≥ 3 esophagitis occurred in less than 7% of patients. The rate of late esophagitis was not directly correlated with dose, but it may be related to the volume of the esophagus treated.

Data in support of proton therapy in early stage NSCLC:

1. Shioyama reported the clinical outcome of 28 patients with stage I NSCLC treated with proton radiotherapy to the median fraction of 3 Cobalt Gray Equivalent (CGE) (range 2-6 CGE) and to a median total dose of 76 CGE (range 49-93 CGE). The 5-year overall survival rate was 70% with local control of 89% for stage IA. However, for stage IB, the local control was 39% and the 5-year overall survival was 15%. Only one case of grade 3 acute toxicity and little late toxicity was observed. In this study, the clinical outcome for stage IA patients was comparable to surgical resection. However, for stage IB patients, the result was much worse than surgical resection and 21% patients recurred in the mediastinum. Since PET scanning was not used for clinical staging, it is possible that the group of patients with stage IB was understaged and significant tumor volume was missed.

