In summary, the standard radiotherapy dose for early stage NSCLC is about 66 Gy with 2 Gy/fraction. However, more than 50% of cancers recur locally. Based on RTOG 9311, which used photon radiotherapy, 90.3 Gy at 2.15 Gy/fraction in patients with lung V20 <25% (mostly early stage lung cancer) was not considered acceptable due to toxicity: Fifteen percent of the patients experienced grade ≥ 3 pneumonitis and there was one case of grade 5 esophagitis. Preliminary data from proton therapy revealed a much lower toxicity profile and promising local control comparable to surgical resection in stage IA patients. However, the reported total doses and fraction sizes of proton radiotherapy varied significantly. The doses used ranged from 70 Gy to 94 Gy and the fraction sizes ranged from 2 Gy to 6 Gy. In many centers, the dose and fraction size were chosen based on the access to the proton facility. Although hypofractionated radiotherapy showed promising results in the literature mentioned above, more clinical studies with long term follow up are needed since hypofractionated radiotherapy is considered to have possible higher long term toxicities, particularly for centrally located lesions.

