9.0 Statistics

The local control rate at 2 years is 50% with historical photon data. We anticipate that proton therapy will increase the local control rate to 75%. With a sample of 40 patients we will have 93% power to detect an increase in the local control rate at 2 years from 50% to 75% with a 1-sided significance level of 5%. This calculation assumes that we will accrue 20 patients per year for 2 years and that we will follow all patients for 2 years. We will estimate the local control rate at 2 years with a 95% confidence interval using the Kaplan-Meier product-limit estimator.

With current photon therapy using similar relative biological effectiveness (RBE) the rate of grade 3 acute pneumonitis is less than 15%, and the chronic pneumonitis rate is 15%. With a sample of 40 patients we will have 81% power to detect a decrease in the rate of grade 3 acute pneumonitis from 15% to 3.75% with a 1-sided significance level of 5%. We will estimate the

grade 4 acute pneumonitis rate with an exact binomial 95% confidence interval.

We will enroll and evaluate a maximum of 40 patients at a rate of 20 patients per year. We will monitor the rate of grade 3+ pneumonitis, which is assessed within 3 months following completion of therapy. Our target grade 3+ pneumonitis rate is 10% or less, based on RTOG Study 9311. We assume a beta(0.2, 1.8) prior distribution for this toxicity rate. This prior distribution has a mean of 10% and a standard deviation of 17%.

We will stop the trial early if $P(\text{grade 3+ pneumonitis} > 10\% \mid \text{data from the trial}) > 0.925$. That is, given the outcomes from the patients who have already been evaluated, if we determine that there is more than a 92.5% chance that the grade 3+ pneumonitis rate is more than 10% we will stop the trial. This decision rule gives the following stopping rule. Stop the trial if

$$\begin{aligned}
 & [\# \text{ of pts with grade 3+ pneumonitis} / \# \text{ of pts evaluated}] \\
 & \geq 4/15, 5/17, 6/24, 7/31, 8/38
 \end{aligned}$$

The operating characteristics of this monitoring rule are shown in Table 1.

Grade 3+ Pneumonitis Rate	Probability of Stopping Early	Sample Size		
		P ₂₅	P ₅₀	P ₇₅
0.050	0.012	40	40	40
0.075	0.053	40	40	40
0.100	0.131	40	40	40
0.150	0.413	21	40	40
0.200	0.709	15	22	40
0.250	0.895	15	15	25
0.300	0.970	15	15	16

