Once we have completed the study we will estimate the grade 3+ pneumonitis rate with a 90% credible interval. If we have grade 3+ pneumonitis in 4 of the 40 patients (10%), then our 90% credible interval for the grade 3+ pneumonitis rate will be 3.7% to 18.5%. If we have grade 3+ pneumonitis in 2 of the 40 patients (5%), then our 90% credible interval for the grade 3+ pneumonitis rate will be 1.1% to 11.8%.

In addition, if there is any grade 4 or 5 toxicity directly caused by proton therapy, the trial will be re-evaluated and decision will be made about modification of treatment or stopping the trial.

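### Neither safety trigger in section 9.0 can respond to grade 3 pneumonitis that appears more than 3 months after radiotherapy

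*Combined protocol and SAP*

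**What the plan says.** Section 9.0 contains two trial-level safety triggers.

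- **Stopping rule.** Its scope is set by this sentence: "We will monitor the rate of grade 3+ pneumonitis, which is assessed within 3 months following completion of therapy". The target is 10% or less, and the boundaries are 4/15, 5/17, 6/24, 7/31 and 8/38.
- **Re-evaluation clause.** The last paragraph adds that "if there is any grade 4 or 5 toxicity directly caused by proton therapy, the trial will be re-evaluated". It has no time limit and covers any organ, but it needs grade 4 or 5.

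On late toxicity, section 2.0 says of the photon dose-escalation study that "acute toxicity rates were acceptable for dose up to 90.3 Gy", and then: "However, late toxicities were more pronounced". It continues: "Late grade ≥ 3 radiation pneumonitis occurred at a rate of 15% for patients with a V20<25" per cent, at 77.4 Gy or above. Section 9.0 repeats the benchmark, stating that with photons "the rate of grade 3 acute pneumonitis is less than 15%, and the chronic pneumonitis rate is 15" per cent. Primary goal 2 in section 1.0 names chronic as well as acute toxicity.

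Late events are collected. Section 5.2 plans visits and chest CT about every 3 months for two years and an analysis of chronic grade ≥ 3 toxicity. Section 6.0 provides for long-term lung evaluation. Neither section says how many late events would prompt a review of the trial. The criteria for going off treatment in section 5.2 concern the individual patient and require grade 4.

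**The concern.** A patient with grade 3 pneumonitis at, say, month 6 is too late for the first trigger and not severe enough for the second. The count of such patients can grow without the plan ever calling for a decision.

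At 20 patients a year over two years, late events in early patients can surface while others are still being enrolled. If acute pneumonitis is as low as the design hopes but late pneumonitis is not, enrolment would run to 40 almost every time. Any review would then depend on an event reaching grade 4 or on ad hoc judgement.

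**Working it through.** **1. Reproduce the printed rule.** Inputs from section 9.0: prior beta(0.2, 1.8), limit 10%, threshold 0.925. The boundary at n patients is the smallest x for which 1 − BetaCDF(0.10; 0.2 + x, 1.8 + n − x) exceeds 0.925. Examples: 4/16 gives 0.9352 (stop), 4/17 gives 0.922 (continue) and 5/17 gives 0.9786 (stop). The required count is 4 at n = 15–16, 5 at 17–23, 6 at 24–30, 7 at 31–37 and 8 at 38–40, which matches the plan. An exact binomial recursion over n = 15 to 40 gives:

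| True 3-month rate | Plan's table | Recomputed |
|---|---|---|
| 5% | 0.012 | 0.011 |
| 10% | 0.131 | 0.135 |
| 15% | 0.413 | 0.422 |

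The rule is calculated correctly. The issue is which events it counts.

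**2. Stress case.** Acute 3.75% is the plan's own alternative, and late 15% is its chronic photon benchmark. Expected late events: 40 × 0.15 = 6. The recursion at 3.75% gives a stopping probability of 0.0035. That figure is the same at any late rate, because late events are not counted.

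**3. What the grade 4–5 clause adds.** If a fraction f of late events reaches grade 4 or more (assumption), the clause fires with probability 1 − (1 − 0.15f)^40. This is 0.26, 0.45 and 0.78 for f = 5%, 10% and 25%, and 0 if f = 0.

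**4. Timing.** One patient enters every 12/20 = 0.6 months. Treatment takes 87.5/2.5 = 35 fractions at 5 a week, so 7 weeks or about 1.6 months. The 15th patient completes the 3-month evaluation at about 15 × 0.6 + 1.6 + 3 = 13.6 months, when about 13.6 × 20/12 ≈ 23 patients are enrolled. There is still enrolment left to protect.

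**5. A cumulative count at the same boundaries.** Simulated trials count grade 3+ pneumonitis at any time to date among patients already evaluated for the 3-month rule. Acute events are counted at that evaluation, and there is no loss to follow-up. Onset of late events is an assumption: the base case is uniform over 3–12 months after radiotherapy. In the stress case:

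| Late onset | Review before last enrolment | Review at any time |
|---|---|---|
| Uniform 3–12 months (base) | 0.352 | 0.544 |
| 6 months | 0.421 | 0.569 |
| 9 months | 0.258 | 0.514 |
| 12 months | 0.121 | 0.492 |
| Uniform 3–24 months | 0.104 | 0.492 |

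When review comes before enrolment closes, a median of 11 patients (6 to 13 across onset assumptions) are not yet enrolled.

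**6. Other rates, base onset.**

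| Acute + late | Before last enrolment | Any time |
|---|---|---|
| 3.75% + 10% | 0.159 | 0.243 |
| 0% + 15% | 0.151 | 0.294 |
| 3.75% + 6.25% (cumulative 10%) | 0.058 | 0.080 |
| 3.75% + 3.75% | 0.024 | 0.029 |

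At 7.5% + 7.5%, the probability of a review at any time is about 0.35 (about 0.28 with onset spread over 3–24 months).

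**The case against.** **The plan does not call a 15% late rate unacceptable.** A reader might infer that it does, or that the 3-month rule could pass a regimen the plan itself calls too toxic. The documents do not support this. Section 2.0 ties the late 15% to 77.4 Gy or above, yet accepts 83.8 Gy in 39 fractions, which lies in that band. It describes 90.3 Gy as "not considered acceptable due to toxicity: Fifteen percent of the patients experienced grade ≥ 3 pneumonitis", but gives no time window there and adds a grade 5 esophagitis. An event of that grade, if caused by protons, would set off the re-evaluation clause. This objection stands, and 15% is used here only as a stress value.

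**The stress case is selective.** It joins a proton hope for acute events to an unimproved photon rate for late ones. The 15 patients already treated at this dose (median follow-up 16.5 months) had no reported grade 3 pneumonitis. At a true 15%, ignoring incomplete follow-up, that has probability 0.85^15 = 0.087, and the 95% upper limit for 0/15 is 21.8%. A late problem is therefore neither supported nor excluded. If acute rates ran at 10–15%, the printed rule would itself fire with probability 0.13 to 0.42. This stands as a limit on likelihood. It does not close the gap.

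**The boundaries were built for 3-month events.** Applied to a cumulative count with unequal follow-up, they lose their posterior meaning. This also stands, so they can serve only as a prompt for review. The 35% review rate at 7.5% + 7.5% is less of a fault than it looks: the cumulative rate there is 15%, above the plan's 10% target.

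**Late events arrive too late to help.** This is partly true. With onset at 12 months, review before the last enrolment has probability only 0.12.

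**Extension to late esophagitis.** A reader might also want a trigger for it. The documents give no target rate from which to set one, so none is proposed.

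**Conclusion.** The gap follows from the wording of the two triggers and needs no assumption about rates. It is confined to grade 3 pneumonitis after 3 months, since late grade 4–5 events caused by protons are already covered. The documents do not define where acute ends and late begins. If the photon study used an earlier cut-off, some of its late cases would fall inside the 3-month window, but later ones would still be missed.

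The size depends on the late rate, which is unknown for this regimen. The added count helps to a moderate degree when late pneumonitis is frequent and appears within a year. It helps little when onset is later, and deaths or loss to follow-up would reduce it further. This is a worthwhile, inexpensive improvement. It is not evidence that the regimen is unsafe, and the 3-month rule does what the plan says it does.

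**What to change.** Leave the 3-month stopping rule unchanged and add to the final paragraph of section 9.0:

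> The trial will also be re-evaluated, but not automatically stopped, if the number of patients with grade 3+ pneumonitis at any time to date, among those already evaluated for the 3-month rule, reaches 4/15, 5/17, 6/24, 7/31 or 8/38. These boundaries serve here only as a prompt for review. Because follow-up is unequal, they carry no posterior probability statement for the cumulative count.

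The sponsor may prefer a different limit for the cumulative count. The cost is a short change to the protocol text and one running tally from visits already scheduled, with no new patients, visits or tests. The other cost is the occasional unneeded review, at the frequencies given in step 6 of the working. A review after enrolment closes can guide only follow-up and later use of the dose.
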